1.2 Rationale

Drug delivery platforms are an innovative exciting advancement in ophthalmology. They allow patients to eliminate topical medications which are generally associated with lack of compliance, difficulty of use and requiring help from family members. These delivery systems can be applied easily in office, and patients do not have to worry about drop insertion in their post-operative regimen.

The results of this research project should help to answer the following question: Does the use of a physician administered intracanalicular dexamethasone insert improve the signs and symptoms of ocular allergy and dry eye disease in KC patients compared to the use of topical loteprednol etabonate ophthalmic gel 0.38%?

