1.2.1 Rationale for Study Design

This prospective study will use a fellow-eye design for 20 participants (40 eyes) with bilateral keratoconus, wearing RGP contact lenses in both eyes, who have been diagnosed with bilateral allergic conjunctivitis and underlying dry eye disease. Per participant, one eye will be randomized to receive the intracanalicular dexamethasone insert at the baseline visit (study eye), while the other eye will be assigned to receive the standard of care topical lotemax etabonate ophthalmic gel 0.38% (control eye). Thus, for every eye in the study group, there will be a paired eye with similar baseline characteristics in the control group sourced from the same participant. The fellow-eye design allows for greater control of potential confounders tied to participants' systemic and ocular health.

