2. STUDY OBJECTIVES

2.1 Primary Objective

To determine the effect of dexamethasone intracanalicular insert through Day 90 as measured by:

- Mean change in itching score from Baseline measured at all visits (Visits 1-5)
 - Graded on a scale of 0-4 and determined by asking the patient
- Mean change in palpebral conjunctivitis papillae score from Baseline measured at all visits (Visits 1-5)
 - Graded using the Papillae Efron Scale as graded by the physician
- Mean change in conjunctival injection score from Baseline measured at all visits (Visits 1-5)
 - Graded on a scale of 0-4 as graded by the physician
- Mean change in corneal staining score from Baseline measured at all visits (Visits 1-5)
 - Graded using the NEI Fluorescein Staining Scale as graded by the physician

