3. STUDY DESIGN

3.1 Study Description and Duration

This prospective, open-label, single-center, randomized, fellow-eye, investigator-sponsored clinical study seeks to investigate the safety and efficacy of the dexamethasone insert in the treatment of allergic conjunctivitis and DED signs and symptoms in patients with Keratoconus using RGP contact lenses when compared to topical standard of care loteprednol etabonate ophthalmic gel 0.38%. After screening a given patient for inclusion and exclusion criteria, and gaining informed consent, one eye will be randomized to receive the dexamethasone insert as determined by a coin flip at the screening visit. The remaining eye will be prescribed a loteprednol etabonate ophthalmic gel 0.38% following a 4,3,2,1 weekly taper. Per enrolled eye, the study period will last for approximately 90 days, consisting of five visits. At Screening/ Baseline, Day 0, Day 7, Day 30 and Day 90, primary and secondary endpoints will be assessed alongside standard-of-care procedures. Adjusting for enrollment period, the study will last a total of approximately 3 months. An abstract with preliminary results will be submitted by May 2020 for the AAOpt conference.

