5. STUDY SCHEDULE OF EVENTS AND VISIT DESCRIPTIONS

5.1 Schedule of Events

Study assessments and procedures are presented by visit in Table 1.

Table 1 Schedule of Events

Study Procedure	Screening/ Baseline	Insertion Visit Day 0	Day 7	Day 30	Day 90	Early Termin ation
Visit	VISIT 1	VISIT 2	VISIT 3	VISIT 4	VISIT 5	
Windows for Visits	(Day -30 to - 1)		(+/- 2 days)	(+/- 3 days)	(+/- 3 days)	
Inclusion/Exclusion	X					
Informed Consent	X					
Demographics	X					
Medical History and Concurrent Illnesses	X					
Concomitant Medications	X	X	X	X	X	X
Uncorrected Distance VA testing (ETDRS at 4m)	X	X	X	X	X	X
MR/BCVA (ETDRS at 4m)	X	X	X	X	X	X
Ophthalmic Examination (with or without dilation)	X	X	X	X	X	X
QOL Assessment (OSDI questionnaire)	X	X	X	X	X	X
Osmolarity (Needs to be done prior to any drop instillation)	X	X	X	X	X	X
MMP9 (Needs to be done prior to any drop instillation)	X	X	X	X	X	X
Grading of itching (Scale 0-4)	X	X	X	X	X	X
Papillae conjunctivitis assessment (Efron Scale)	X	X	X	X	X	X
Conjunctival Injection (Scale 0- 4)	X	X	X	X	X	X
Corneal staining (NEI Fluorescein Scale)	X	X	X	X	X	X
TBUT	X	X	X	X	X	X
Intraocular Pressure (IOP)	X	X	X	X	X	X
Intracanalicular dexamethasone insert*		X				
Insert Visualization		X	X	X	X	X
Subject reported AEs after insertion		X	X	X	X	X
Physician ease of insertion as measured on a 0-10 point scale		X				

COMTOL					X	X
--------	--	--	--	--	---	---

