5.2 Study Visit Descriptions

5.2.1 Study Procedures

Screening/Baseline (Visit 1)

After the patient has provided informed consent, the following information will be collected:

- Inclusion/Exclusion
- Demographics
- Medical History and Concurrent Illnesses
- Concomitant Medications
- Uncorrected and best-corrected visual acuity with manifest refraction as measured by ETDRS chart at 4 meters
- Ophthalmic Examination (with or without dilation)
- QOL assessment as measured by OSDI questionnaire
- Osmolarity (Needs to be done prior to any drop instillation)
- MMP9 (Needs to be done prior to any drop instillation)
- Grading of itching (scale 0-4)
- Papillae conjunctivitis assessment (Efron Scale)
- Conjunctival Injection
- Corneal Staining
- TBUT
- Intraocular Pressure

Insertion Visit/Day 0 (Visit 2)

- Concomitant Medications
- Uncorrected and best-corrected visual acuity with manifest refraction as measured by ETDRS chart at 4 meters
- Ophthalmic Examination (with or without dilation)
- QOL assessment as measured by OSDI questionnaire
- Osmolarity (Needs to be done prior to any drop instillation)
- MMP9 (Needs to be done prior to any drop instillation)
- Grading of itching (scale 0-4)
- Papillae conjunctivitis assessment (Efron Scale)
- Conjunctival Injection
- Corneal Staining
- TBUT
- Intraocular Pressure
- Insertion of Dextenza (intraocular dexamethasone insert)
- Insert Visualization
- Subject reported AEs after insertion
- Physician ease of insertion grading

Day 7 (Visit 3)

- Concomitant Medications

- Uncorrected and best-corrected visual acuity with manifest refraction as measured by ETDRS chart at 4 meters
- Ophthalmic Examination (with or without dilation)
- QOL assessment as measured by OSDI questionnaire
- Osmolarity (Needs to be done prior to any drop instillation)
- MMP9 (Needs to be done prior to any drop instillation)
- Grading of itching (scale 0-4)
- Papillae conjunctivitis assessment (Efron Scale)
- Conjunctival Injection
- Corneal Staining
- TBUT
- Intraocular Pressure
- Insert Visualization
- Subject reported AEs after insertion

Day 30 (Visit 4)

- Concomitant Medications
- Uncorrected and best-corrected visual acuity with manifest refraction as measured by ETDRS chart at 4 meters
- Ophthalmic Examination (with or without dilation)
- QOL assessment as measured by OSDI questionnaire
- Osmolarity (Needs to be done prior to any drop instillation)
- MMP9 (Needs to be done prior to any drop instillation)
- Grading of itching (scale 0-4)

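### The primary endpoints are change from a Baseline labelled at the screening visit, where eyes are selected, and no passage makes the between-eye difference in change the primary estimator

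*Combined protocol and SAP*

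**What the plan says.** **Endpoints.** Section 2.1 opens with "To determine the effect of dexamethasone intracanalicular insert through Day 90 as measured by" and lists four scores: itching, papillae, conjunctival injection and corneal staining. Each is worded like the first, "Mean change in itching score from Baseline measured at all visits (Visits 1-5"). The synopsis repeats the list.

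**Comparator.** Section 1.2 asks whether the insert will "improve the signs and symptoms of ocular allergy and dry eye disease in KC patients compared to the use of topical loteprednol" gel. The synopsis objective and section 3.1 also name that comparison. Section 2.1 does not.

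**Visits.** Table 1 and section 5.2.1 call Visit 1 Screening/Baseline, with a window of Day -30 to -1. Visit 2 is Day 0, the insertion visit. Section 3.1 treats them as separate assessments: "At Screening/ Baseline, Day 0, Day 7, Day 30 and Day 90, primary and secondary endpoints will be assessed". All four scores are scheduled at both visits. The Day 0 list in section 5.2.1 places them before "Insertion of Dextenza (intraocular dexamethasone insert").

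**Selection.** Table 1 checks eligibility at Visit 1 only. Section 4.1.1 requires, bilaterally, an Efron papillae score of at least 1, symptoms of itching and an NEI staining score of at least 1. Injection is not an entry criterion.

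**Timing of allocation and treatment.** Section 3.1 says that "one eye will be randomized to receive the dexamethasone insert as determined by a coin flip at the screening visit". Section 1.2.1 says that "one eye will be randomized to receive the intracanalicular dexamethasone insert at the baseline visit (study eye"). Table 1 marks the row "Intracanalicular dexamethasone insert" at Visit 2 only. Neither Table 1 nor the visit lists show when the control gel starts.

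**The concern.** Taken as written, section 2.1 describes a within-eye change from the visit at which the eye had to score high enough to enter. Scores that vary between visits will on average be lower at the next visit in eyes selected this way, with no treatment effect at all. A mean fall in the insert eye would then be partly an artefact of selection.

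Two of the five visits named in the endpoint carry no information on the insert: Visit 1 is the reference itself, and Visit 2 is scored before insertion if the list order is followed.

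The randomised fellow-eye design protects against the artefact, but only if the between-eye difference is what is analysed as primary. Section 2.1 does not say so, and there is no statistical analysis section to settle it. Either a within-eye or a between-eye result could be reported as the primary finding.

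**Working it through.** **1. Is there a plan figure to reproduce?** No. The only design figure is 20 patients (40 eyes). The documents give no alpha, power, effect, SD or correlation, so every input below is assumed.

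**2. What each visit contributes.** With Visit 1 as Baseline:
- Visit 1: score minus itself = 0.
- Visit 2: Day 0 score minus Visit 1 score, with no insert effect if scoring precedes insertion.
- Visits 3, 4 and 5 (Days 7, 30, 90): the only visits after insertion.

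**3. Regression to the mean within the eye.** Model: a normal latent score rounded to 0-4 (Efron range assumed), both eyes at least 1 at Visit 1, no treatment effect, a coin flip to choose the insert eye, and constant test-retest correlation r. Noise at a visit is either shared between eyes (stable and visit parts each correlated 0.6) or independent between eyes (total between-eye correlation 0.6, or 0.5 when r = 0.5). There were 600,000 simulated patients per scenario. Mean within-eye change from Visit 1, SD 1:

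| Pre-selection mean | Share eligible | Enrolled Visit 1 mean | Shared noise, r = 0.5 / 0.7 / 0.9 | Independent noise, r = 0.5 / 0.7 / 0.9 |
|---|---|---|---|---|
| 1.0 | 55-56% | 1.63 | -0.31 / -0.20 / -0.09 | -0.21 / -0.14 / -0.07 |
| 1.5 | 75-76% | 1.87 | -0.19 / -0.12 / -0.05 | -0.13 / -0.08 / -0.04 |
| 2.0 | 89% | 2.18 | -0.10 / -0.06 / -0.03 | -0.06 / -0.04 / -0.02 |

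With SD 0.8 the falls run from 0.01 to 0.24. In every scenario the change from Day 0 and the between-eye difference in change (from either visit) are within 0.005 of zero.

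A cross-check for one eye without rounding: fall = SD × (1 - r) × φ(a)/(1 - Φ(a)), with a = (1 - mean)/SD. At mean 1, SD 1, r = 0.5, a = 0 and the fall is 0.5 × 0.798 = 0.40. At mean 2, SD 1, r = 0.9 it is 0.03. Direction and order of magnitude agree.

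The model fits papillae. It fits itching only if symptoms mean a score of at least 1. It does not fit the NEI total, which sums several areas, and injection is not a selection score.

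**4. Illustrative false-positive rate.** The documents name no test. For an assumed two-sided 5% one-sample t-test on 20 insert eyes, SD 1, with no treatment effect, change from Visit 1 rejects in about 5% to 28% of trials. Change from Day 0 rejects in 4.4% to 5.6%, and between-eye change from Visit 1 in 4.4% to 5.5%.

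**5. Precision of the between-eye contrast.** Suppose correlation falls by a factor of 0.7 per 30 days and single-score reliability R is 0.6 to 1.0. For outcome day d and screening s days before Day 0, the ratio of standard errors (Visit 1 baseline to Day 0 baseline) is

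sqrt[(1 - R × 0.7^((d+s)/30)) / (1 - R × 0.7^(d/30))].

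For s = 30:
- Day 7: R = 1 gives sqrt(0.3559/0.0799) = 2.11; R = 0.6 gives sqrt(0.6135/0.4479) = 1.17.
- Day 30: R = 1 gives sqrt(0.51/0.30) = 1.30; R = 0.6 gives sqrt(0.706/0.58) = 1.10.
- Day 90: R = 1 gives sqrt(0.7599/0.657) = 1.08; R = 0.6 gives sqrt(0.8559/0.7942) = 1.04.

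At Day 30 the loss is 3% to 9% for screening at Day -7 and 0% to 1% at Day -1. If correlation does not decay with time, there is no loss.

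**6. The timing passages side by side.** Screening/Baseline is one visit, so a coin flip at screening (3.1) and randomisation at the baseline visit (1.2.1) agree. The conflict arises if 1.2.1 is read as giving the insert at the baseline visit, because Table 1 gives it at Day 0. Section 3.1 mentions the gel prescription straight after the coin flip but gives no start day. The documents therefore do not show that both eyes are untreated when scored at Day 0.

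**The case against.** **The comparison is stated.** The synopsis objective, 1.2 and 3.1 all ask about insert versus loteprednol, and the design is a randomised fellow-eye one. A reader might infer from section 2.1 that the trial has no stated comparison; that goes too far. What is missing is narrower: the between-eye difference in change as primary estimator, and the visit or visits at which it is taken.

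**The randomised contrast is sound.** A reader might infer that selection at screening biases the comparison with loteprednol. It does not: both eyes must qualify and a coin flip assigns them, so the fall is the same in expectation in each eye. This objection stands in full.

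**Baseline may not mean Visit 1.** The label in Table 1 and 5.2.1, and the separate listing in 3.1, point to Visit 1. But no passage defines the term, and 1.2.1 can be read as Day 0. This stands as a reason to define baseline, not as a reason to leave it.

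**Visits 1-5 may be only a measurement schedule.** That is a fair reading. No passage averages change over the five visits, so a claim that the treatment effect is diluted by averaging in Visits 1 and 2 is not supported.

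**Day 0 might be the worse baseline.** If the gel starts before Day 0 scoring, a Day 0 baseline would bias the between-eye contrast and Visit 1 would not. This stands, and it is why the timing must be settled first.

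**Conclusion.** The point holds, at a modest level, and should be fixed. Under the labelled Baseline, the within-eye change that section 2.1 literally describes includes regression to the mean for the scores used at entry. The assumed model with SD 1 puts this at about 0.02 to 0.3 grade. The upper end needs a pre-selection mean of 1.0, r = 0.5 and noise shared between eyes, and the documents do not favour any one scenario. The figure applies to papillae and, conditionally, to itching. It gives no size for staining and does not concern injection.

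The between-eye contrast is unbiased with a Visit 1 baseline. Its only possible cost is precision: with screening at Day -30 and the assumed decay, the standard error is 17% to 111% larger at Day 7, 10% to 30% at Day 30 and 4% to 8% at Day 90. The cost is smaller for later screening and nil without decay.

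The documents do not support saying that Day 0 is simply the right baseline. It is valid for the contrast only if neither eye has been treated when it is scored.

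**What to change.** 1. Reconcile 1.2.1, 3.1 and Table 1 on the visit of insertion, and state when the control gel starts relative to the Day 0 scoring.
2. Define baseline for both eyes as the last score taken before either eye is treated. This is the Day 0 score, recorded before insertion, if both eyes are still untreated then. State that order for the Day 0 visit.
3. Keep Visit 1 for eligibility, and name Visits 3-5 (Days 7, 30 and 90) as the outcome visits.
4. State in 2.1 and the synopsis that the primary contrast is the paired difference between insert eye and loteprednol eye in change from that baseline.

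The cost is endpoint wording and a stated order of procedures. All four scores are already scheduled at Day 0, so no visit or test is added.

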2.2 Secondary Objectives

To determine the effect of dexamethasone, insert through Day 90 as measured by:

- Physician ease of insertion as measured by a 0-10-point scale
- Vision-related Quality of Life (QOL) assessment as measured with OSDI Questionnaire measured at all visits (Visits 1-5)
- Uncorrected and corrected VA mean change from Baseline measured at all visits (Visits 1-5)
- Patient's therapy of preference as measured by the Comparison of Ophthalmic Medications for Tolerability Questionnaire (COMTOL) at final visit (Visit 5)
- Mean change in MMP9/osmolarity from Baseline measured at all visits (Visits 1-5)

- Incidence of IOP spikes (IOP increased \geq 10mmHg from baseline)

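### The OSDI is the plan's only dry-eye symptom measure; if scored once per patient, it cannot separate insert from gel when each patient has both

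*Combined protocol and SAP*

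**What the plan says.** Section 1.2 asks whether the insert will "improve the signs and symptoms of ocular allergy and dry eye disease in KC patients compared to the use of topical loteprednol etabonate" gel. The synopsis objective says the same, and section 3.1 again names "treatment of allergic conjunctivitis and DED signs and symptoms in patients with Keratoconus using RGP contact lenses when compared to topical standard of care" loteprednol. The question is therefore comparative and includes dry-eye symptoms.

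Treatment is allocated by eye. Section 1.2.1 states "This prospective study will use a fellow-eye design for 20 participants (40 eyes"). Section 3.1 says "one eye will be randomized to receive the dexamethasone insert as determined by a coin flip at the screening visit", and then "The remaining eye will be prescribed a loteprednol etabonate ophthalmic gel 0.38% following a 4,3,2,1 weekly taper". No patient receives only one of the two treatments.

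Section 2.2 opens its list with "To determine the effect of dexamethasone, insert through Day 90 as measured by" and includes "Vision-related Quality of Life (QOL) assessment as measured with OSDI Questionnaire measured at all visits (Visits 1-5"). Section 4.1.1 makes dryness on the OSDI part of the dry-eye entry definition, alongside staining and TBUT, so the plan itself treats the OSDI as its dryness measure. Appendix V gives the form only as an attachment, which is not in the text available for review.

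**The concern.** The fellow-eye design is justified in section 1.2.1 on the ground that "for every eye in the study group, there will be a paired eye with similar baseline characteristics in the control group sourced from the same" person. That protection reaches only outcomes recorded separately for each eye. An outcome recorded once per person has no paired control value.

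Section 2.2 labels the OSDI a vision-related quality-of-life assessment and gives no by-eye instruction. A report that followed the section's heading could present a fall in OSDI as an effect of the insert when some or all of it came from the gel, the season or the natural course of the disease. The dry-eye symptom part of the study question would have no between-treatment measure behind it.

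**Working it through.** The plan gives no alpha, power, effect size or standard deviation and has no statistical analysis section, so there is no planned calculation to reproduce. The question is whether the contrast can be estimated at all.

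**Step 1. Is there another dry-eye symptom measure?**

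| Measure | Where | Why it does not fill the gap |
|---|---|---|
| Itching, 0-4 | 2.1, Appendix I | Patient-reported, but section 4.1.1 uses it to define allergic conjunctivitis |
| COMTOL | 2.2, Table 1 | Therapy preference at the end of the study, with no baseline |
| Staining, TBUT, osmolarity, MMP9 | 2.1, 2.2, Table 1 | Signs or tests, not symptoms |
| OSDI | 2.2, 4.1.1, Table 1 | The only dryness symptom measure; no by-eye instruction |

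**Step 2. One score per patient.** Let *a* be the change due to the insert and *b* the change due to the gel. With one OSDI change per patient, the design matrix has columns for intercept, insert received and gel received. All 20 patients have the row (1, 1, 1), so the rank is 1 of 3. The contrast insert minus gel is (0, 1, -1). Its product with (1, 1, 1) is 0 + 1 - 1 = 0, so it lies outside the row space and is not estimable. Adding patients only adds identical rows.

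As an illustration, assume the score reflects the average of the two eyes, (*a* + *b*)/2:

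| *a* (insert) | *b* (gel) | Mean OSDI change | *a* - *b* |
|---|---|---|---|
| -20 | 0 | -10 | -20 |
| -10 | -10 | -10 | 0 |
| 0 | -20 | -10 | +20 |

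The same observed change fits a large benefit of the insert, no difference, and a large benefit of the gel.

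**Step 3. Does the coin flip help?** It decides only which side gets the insert. Suppose the score weights the right eye by *w*R and the left by *w*L. Patients with the insert on the right average *w*R·*a* + *w*L·*b*; those with it on the left average *w*L·*a* + *w*R·*b*. The difference is (*w*R - *w*L)(*a* - *b*). This is zero with equal weights. With unequal weights it cannot be turned into *a* - *b* unless the weights are known, and the plan gives none.

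**Step 4. One score per eye.** With 20 patient effects and one treatment effect, the 40 eye-level rows give rank 21 of 21, so the contrast is estimable.

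For scale, assume two-sided alpha 0.05 and 80% power, and let *d* be the mean within-patient difference divided by its standard deviation. With 20 complete pairs the detectable *d* is (1.960 + 0.842)/√20 = 2.802/4.472 = 0.63 by the normal formula, or 0.66 with the paired t-test. From n = (2.802/*d*)², rounded up:

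| *d* | 0.3 | 0.4 | 0.5 | 0.6 | 0.7 | 0.8 |
|---|---|---|---|---|---|---|
| Pairs needed | 88 | 50 | 32 | 22 | 17 | 13 |

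**The case against.** The strongest objection is that the form cannot be seen. No sentence in the protocol says that the OSDI yields one score per person, and if the attached version were completed by eye the point would fall. This stands as a condition. What the text offers is the quality-of-life label, the lack of any by-eye instruction, and the appendix list, which marks the COMTOL as adapted but not the OSDI. A reader might also take the single OSDI row in Table 1 as proof of whole-patient scoring. It is not: IOP, staining and TBUT are eye-level measures and have a single row too.

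Second, the heading in section 2.2 is loose. It also covers ease of insertion and therapy preference, and the OSDI line does not mention change from baseline or a comparison. A reader might infer that the plan intends to credit the insert with the OSDI change. The documents do not say so; the heading only invites that reading.

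Third, a reader might infer that the trial cannot answer its question. That goes too far. The question joins signs and symptoms of two conditions, the OSDI is secondary, and dry-eye signs can be compared between eyes.

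Fourth, a new dryness item would be unvalidated, and patients will know which eye has the insert. That is a real weakness, but a biased contrast whose limits can be stated is still more informative than no contrast. Naming TBUT as an endpoint is optional; it is a sign and leaves the symptom gap open.

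**Conclusion.** The concern holds on one condition: that the attached OSDI is scored once per patient, with no known weighting of one eye over the other. Nothing in the text suggests otherwise, but the sponsor should confirm it. On that condition the OSDI gives a joint, uncontrolled before-after change under both treatments and no estimate of insert minus gel at any sample size. The conclusion does not depend on the averaging illustration, or on alpha, power or the choice of 20 patients.

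The reach is one secondary endpoint and the dry-eye symptom component of the question. The four primary endpoints and the dry-eye signs are not affected by this point. The OSDI remains usable for eligibility and as a patient-level description.

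**What to change.** 1. Confirm how the attached OSDI form is completed and scored.
2. If it is scored once per patient, state in section 2.2 and the synopsis that it is a patient-level description of the combined regimen, not attributed to either treatment.
3. Add a patient-reported dryness/discomfort grade on a 0-4 scale, asked separately for the right and left eye at every scheduled visit, including those before treatment so that each eye has its own baseline. List it as a secondary endpoint, defined as the within-patient difference between eyes in change from baseline.
4. When Appendix I is amended to carry this question, also say whether itching is graded by eye, since the present wording does not.

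The cost is one more question per eye at visits already planned, and a protocol amendment that needs IRB approval before use (section 7.4). The item would be unvalidated and exposed to expectation bias in an open-label trial, and 20 pairs would detect only a fairly large standardised difference. The OSDI could no longer be presented as evidence for the insert. The change should precede enrolment, because by-eye ratings cannot be recovered after a visit has passed.
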